5.3. Safety monitoring

A safety review committee (SRC) will convene after every 5th subject with HER2- disease has completed the Ad-RTS-hIL-12 immunotherapy cycle (i.e., after each subject has completed 21 days on study). The SRC will also convene after the first 5 subjects with HER2+ disease have completed the Ad-RTS-hIL-12 immunotherapy cycle. The SRC will consist of the investigator, medical monitor, and other appropriate Sponsor representatives. The SRC will review all available safety information (AEs/SAEs, laboratory parameter data, ECG, etc.). Tolerability will be evaluated separately for subjects with HER2- and HER2+ disease.

5.4. Sample size

A maximum of 40 subjects will be treated. Because this patient population is heterogeneous, it is difficult to define a threshold for a clear null and alternative hypothesis. This sample size will allow us to estimate an overall progression rate at 12 weeks with a maximum 95% exact confidence interval half-width of 0.16. This is based on an exact binomial calculation and is an estimate. However, analysis of progression-free survival will be conducted using Kaplan-Meier methods.

6. STATISTICAL METHODS

This study is designed to evaluate the safety and tolerability of one cycle of Ad-RTS-hIL-12 immunotherapy a) following a first-, second-, or third-line standard treatment in HER2- subjects, or b) together with a first-, second-, or third-line anti-HER2 antibody therapy in HER2+ subjects, thus the safety and efficacy analyses will be performed by HER2 status and overall.

6.1. Protocol Deviations

A protocol deviation is any change, divergence, or departure from the study design or procedures defined in the protocol. Important protocol deviations are a subset of protocol deviations that may significantly impact the completeness, accuracy, and/or reliability of the study data or that may significantly affect a subject's rights, safety, or well-being.

No subject will be removed from any analysis population because of a protocol deviation.

Important protocol deviations include (but are not limited to):

- Deviation from inclusion/exclusion criteria
- Withdrawal criteria met during the study but subject was not withdrawn
- Prohibited concomitant medications.

Important protocol deviations will be identified prior to database lock. Protocol deviations will be listed and summarized by type.

6.2. Analysis Populations

The following subject populations will be evaluated and used for presentation and analysis of the data:

- The safety population will comprise all subjects who have received either the injection of Ad-RTS-hIL-12 or any doses of veledimex
- The veledimex-treated population will comprise subjects who have received the injection of Ad-RTS-hIL-12 and at least one dose of veledimex
- The veledimex-evaluable population will comprise subjects who have received the injection of Ad-RTS-hIL-12 and all 7 doses of veledimex

6.3. Data Handling Conventions

SAS version 9.1.3 or higher will be utilized for all listings and tables.

All listings will be ordered by HER2 status and subject number. Listings will present all available data.

Tables will summarize data for each HER2 status group and overall.

Summary statistics will be provided for continuous variables (e.g., age). Unless otherwise stated, this will consist of the number of subjects with a non-missing value of the variable (n), mean, standard deviation (std dev), median, minimum, and maximum. The same number of decimal places as in the raw data will be presented when reporting the minimum and maximum, 1 more decimal place than in the raw data will be presented when reporting the mean and median, and 2 more decimal places than in the raw data will be presented when reporting the standard deviation.

Frequency counts will be provided for categorical variables (e.g., gender). Unless otherwise stated, this will consist of the number of subjects with a response in a particular category and the percentage

of the total number of subjects in that particular column. Unless otherwise stated, missing responses will be included in both the display and in the calculation of percentages (i.e., they will be included in the denominator). Percentages will be rounded to 1 decimal place.

No imputations for missing or partial data will be made.

Unless otherwise specified, baseline is the last observation before the first administration of study drug.

7. SUBJECT DISPOSITION

Study eligibility, inclusion and exclusion criteria, HER2 status, and population assignment will be listed.

The number and percent of subjects who discontinue from the study will be summarized by reason for discontinuation, HER2 status group, and overall.

The number and percentage of subjects in each analysis population will be tabulated.

Important protocol deviations will be summarized and listed.

8. BASELINE DEMOGRAPHIC CHARACTERISTICS

8.1. Demography

Demographic and baseline disease characteristic data will be summarized. Data to be tabulated will include at least demographic features such as sex, age, and race, as well as disease-specific status and medical history.

Age is taken to be the subject's age on the date of the Screening visit.

Conversions for height and weight are as follows:

$$\text{Height (cm)} = \text{Height (inches)} \times 2.54$$

$$\text{Weight (kg)} = \text{Weight (lb)} \times 0.4536$$

Demographics will be listed and tabulated using descriptive statistics.

8.2. Medical History

Details of prior cancer treatment (chemo-, and immuno-therapies, radiation therapy, surgeries), current primary cancer diagnosis, initial diagnosis of breast cancer, diagnosis of metastatic disease and current disease status will be listed. Time in months since initial diagnosis, grading and type at time of initial diagnosis, and at grading, pathology and HER genotype types at Screening will be tabulated.

Prior cancer treatment information will be tabulated. This will include whether the subject had any previous treatment, treatment type, and the best response from previous treatment.

8.3. Previous and Concomitant Medication

Concomitant medications recorded during the study will be coded using the WHO-Drug version March 2016. Details of concomitant medications will be listed.

Medications will be tabulated according to whether they were being taken prestudy and/or during the study. Medications received in the period preceding consent (~28 days) in addition to those ongoing at Screening will be captured in the Case Report Form (CRF). Concomitant medications are any that were being taken on or after the first dose of study medication until completion of veledimex dosing. If the start and stop dates of the concomitant medications do not clearly define the period(s) during which a medication was taken, it will be assumed to have been a concomitant medication.

Previous and concomitant medications will be tabulated by preferred term and ATC term 2.

Non-pharmacological concomitant measures (e.g., procedures) will be listed.

9. SAFETY

Safety evaluations will be based on the incidence, intensity, and type of AEs and SAEs. Clinically significant changes in the subject's physical examinations, vital signs, ECG evaluations, and abnormal laboratory values will be captured as AEs. AEs, laboratory test results, ECG findings, and vital signs will be tabulated and presented for all subjects in the study, as well as by HER2 status group and CYP450 3A4 drug interacting use. Exposure to study drug and reasons for discontinuation of study treatment will be tabulated.

9.1. Study Drug Exposure

Details of study drug administration and dose modifications will be listed.

9.1.1. Ad-RTS-hIL-12

Total volume received, number of sites, and whether the dose was modified will be tabulated.

9.1.2. Veledimex

Full details of each dose and dose modifications will be listed.

The number of doses received will be tabulated. Data will reflect date and mg of veledimex taken, % compliance (dose held by PI/Sponsor), % compliance (missed dose).

9.2. Adverse Events

AEs will be coded using the Medical Dictionary for Regulatory Activities (MedDRA®) Version 18.1 or higher for purposes of summarization. All AEs occurring during the study will be included in data listings, presented by subject.

Treatment-emergent adverse events (TEAEs) will be summarized. Adverse events will be regarded as TEAEs if they occur during or after administration of the first dose of study drug (either veledimex or Ad-RTS-hIL-12) through the evaluation period for safety (in 6 weeks after first dose), regardless of the relationship to study drug. In addition, any event present at baseline that worsens in intensity or is subsequently considered to be drug related by the investigator will be considered a TEAE.

Summaries of all TEAEs, treatment-related TEAEs, and all SAEs will be tabulated by System Organ Class, Preferred Term, severity, and HER2 status group. For summaries of events, percentages will be calculated from the total number of events per group/dose cohort. For summaries of subjects, percentages will be calculated from the total number of subjects per group/dose cohort. Where a subject has multiple adverse events in a System Organ Class / Preferred Term, only the most severe will be included in summaries.

In addition to the full listing of all AEs, separate listings for AEs, leading to death, and AEs leading to study discontinuation will be presented.

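### SAP 9.2 does not limit its most-severe-event rule to subject counts; read literally, it also drops repeat events from the event-level adverse event tables

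*SAP*

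**What the plan says.** SAP 9.2 (Adverse Events) first names the tables: "Summaries of all TEAEs, treatment-related TEAEs, and all SAEs will be tabulated by System Organ Class, Preferred Term, severity, and HER2 status group". It then gives two denominators. For event counts: "For summaries of events, percentages will be calculated from the total number of events per group/dose cohort". For subject counts: "For summaries of subjects, percentages will be calculated from the total number of subjects per group/dose cohort". The next sentence is the collapsing rule: "Where a subject has multiple adverse events in a System Organ Class / Preferred Term, only the most severe will be included in summaries".

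The rule speaks of summaries in general, the word just used for both kinds of table. The section does not say which kind is meant. It also does not say whether the event total in the denominator is taken before or after the rule is applied.

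The listings are treated separately and are complete: "All AEs occurring during the study will be included in data listings, presented by subject".

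**The concern.** Keeping the worst event per subject and term is the usual convention for subject counts, because each subject should appear once in a row. In an event count it removes what the table exists to show, namely how often events occur, including repeats. An event table that keeps at most one event per subject and term is a subject count under another name.

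A programmer following the text literally would thin the event tables for all treatment-emergent AEs, treatment-related AEs and SAEs. Two SAEs of the same term in one subject would count as one. Because the tables are also split by severity, removing every event except the worst would move the severity mix of the remaining events upward. Another programmer could limit the rule to subject counts and produce different tables from the same plan.

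**Working it through.** The documents give no figure to reproduce here, so the check is direct counting.

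**Inputs**
- The denominators and the collapsing rule: SAP 9.2.
- Maximum sample size, used only to scale the illustration: "A maximum of 40 subjects will be treated" (SAP 5.4).
- Events per subject and term: not given in either document, so assumed.

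**Notation.** E is the number of all events. D is the number of distinct subject-by-term pairs, which is what remains after the rule. m = E/D is the mean number of events per pair. For one term t, the same quantities are E_t, D_t and m_t.

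**Three readings of the event percentage for term t**
1. Numerator thinned, denominator all events: D_t/E. The column sums to D/E = 1/m.
2. Numerator and denominator both thinned: D_t/D. The column sums to 100%.
3. Rule limited to subject summaries: E_t/E. The column sums to 100%.

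**Illustration (assumed counts, 40 subjects).** Term A occurs in 10 subjects with 4 episodes each, B in 20 with 1 each, and C in 10 with 2 each.
- E = 10×4 + 20×1 + 10×2 = 80.
- D = 10 + 20 + 10 = 40.
- m = 80/40 = 2.

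| Term | Reading 1 | Reading 2 | Reading 3 |
|---|---|---|---|
| A | 10/80 = 12.5% | 10/40 = 25.0% | 40/80 = 50.0% |
| B | 20/80 = 25.0% | 20/40 = 50.0% | 20/80 = 25.0% |
| C | 10/80 = 12.5% | 10/40 = 25.0% | 20/80 = 25.0% |
| Sum | 50.0% | 100% | 100% |

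**What does not depend on the denominator.** Term A has 40 events and B has 20, a ratio of 2. Under readings 1 and 2 the ratio becomes 10/20 = 0.5. Whenever the rule reaches event tables, a recurrent term loses ground to a one-off term.

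**What does depend on it.** Relative to its true event share, a term's percentage is multiplied by 1/m_t under reading 1 and by m/m_t under reading 2. For A these are 1/4 (50.0% to 12.5%) and 2/4 (50.0% to 25.0%). Under reading 2 a term with average recurrence, such as C, keeps its share of 25.0%.

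**Range for the column sum under reading 1**

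| Assumed m | 1 | 1.25 | 1.5 | 2 | 3 |
|---|---|---|---|---|---|
| Sum = 1/m | 100% | 80.0% | 66.7% | 50.0% | 33.3% |

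At m = 1 every pair has one event and all three readings agree.

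**Subject tables.** In the illustration these are 10/40 = 25.0%, 20/40 = 50.0% and 10/40 = 25.0% under every reading.

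**The case against.** The best defence is that the rule was meant only for subject summaries. It follows directly after the sentence on subject percentages and is framed per subject: "Where a subject has multiple adverse events in a System Organ Class / Preferred Term". Giving event summaries their own denominator also suggests that two different counts were intended. This is plausible, and under it nothing is wrong. It remains an inference. The sentence carries no limit, and the paragraph refers to dose cohorts although SAP 5.2 describes a single-arm study, so the wording may be generic and is a weak guide to intent.

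The room for repeats may also be small. SAP 5.2 describes one 21-day cycle with one injection and seven days of veledimex, and SAP 9.2 closes the treatment-emergent window at six weeks. Protocol 7.2.2 records a symptom lasting several days as one event at its maximum intensity. That protocol describes a different design from the SAP, so this is only indicative, but it argues against treating consecutive daily symptoms as separate events.

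Three stronger readings are tempting, and the documents do not support them.
- **The event tables cannot add up.** They fall short of 100% only if the rule reaches event summaries, the denominator is counted before the rule, and at least one subject has a repeat event in a term. The SAP leaves the first two open.
- **A term with k episodes per affected subject is understated k-fold.** That holds only under reading 1. Under reading 2 the factor is k/m, and with no repeats there is no effect.
- **The primary safety conclusion is compromised, or recurrences vanish from the report.** SAP 5.2 rests the safety evaluation on related, treatment-refractory Grade 3 and 4 events within 21 days, not on a term's share of all events. The safety review committee sees all available safety information (SAP 5.3). The listings keep every event, and the rule itself keeps each subject's worst grade.

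**Conclusion.** The point holds as a minor defect of specification. As written, the most-severe rule covers event-level summaries. Applied that way it drops repeat events and understates recurrent terms relative to one-off terms, whichever denominator is used. Failure to sum to 100% is a further, conditional consequence.

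The size cannot be derived from the documents, because the number of events per subject and term is not given. The percentages above rest on assumed counts and show the mechanism, not an expected result. No estimate, test or safety decision described in the SAP is shown to change. What is at stake is whether the event-level tables for treatment-emergent AEs, related AEs and SAEs mean what a reader will take them to mean, and whether two programmers would produce the same ones.

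**What to change.** In SAP 9.2, restrict the most-severe rule to subject-level summaries. Add that event-level summaries count every event, repeats included, in both the numerator and the total used as denominator.

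The cost is one clause before database lock, with no new data and no added analysis. If this was always the intention, the edit simply records it.

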9.3. Laboratory Evaluations`

All laboratory parameters will be converted to conventional units, usually SI units, for the purposes of summary. Listings will present the data in the original unit collected, as well as the converted value in conventional units. A separate listing will present all units used for data collection, along with the corresponding units and conversion factors.

Absolute values and change from baseline in clinical laboratory parameters will be summarized by visit and HER2 status group. The incidence of normal and abnormal (subdivided into ‘not clinically significant’ and ‘clinically significant’) laboratory values will be tabulated by visit and HER2 status group.

Pregnancy test data will be listed only.

9.4. Vital signs

Details of vital signs will be listed.

Vital signs parameters include systolic and diastolic blood pressure (mmHg), heart rate (bpm), respiratory rate (breaths/minute), and temperature (°C).

The conversion for temperature is as follows:

$$\text{Temperature } (\text{°C}) = (\text{Temperature } (\text{°F}) - 32) \times 5/9$$

Absolute values and changes from baseline for vital sign parameters will be summarized by visit and HER2 status.

9.5. ECGs

Heart Rate (bpm), PR Interval (ms), QRS complex duration (ms), RR interval (ms), QT interval (ms) and QTc interval (ms) will be summarized for absolute values and changes from baseline (Screening visit) by visit and HER2 status group.

Overall electrocardiogram (ECG) finding categories will be summarized by visit and HER2 status group.

9.6. Body weight

Body weight (kg) will be summarized for absolute values and changes from baseline by visit, HER2 status group, and overall.

9.7. Physical exam

Results of the targeted neurological exam will be listed and summarized by HER2 status group. Physical examination data will be listed.

9.8. ECOG Performance Status

Results of the Eastern Cooperative Oncology Group (ECOG) Performance Status will be listed and will be summarized as a categorical variable by visit, HER2 status group, and overall.

10. EFFICACY

The tumor response will be assessed by RECIST v1.1 and irRC. Full details concerning the use of RECIST v.1.1 may be found in the Appendix 16.3 in the protocol and for irRC can be referred to the Section 9.2.2.7 in the protocol.

10.1. Progression rate

The proportion failed by 12 weeks is denoted as the progression rate, and is derived based on the sum of progression events, death events, and subjects who discontinue the trial due to an AE.

The progression rate will be summarized by HER2 status group and overall for the evaluable population.

An exact 2-sided 95% confidence interval for the proportion of subjects who failed treatment by 12 weeks will also be presented by visit and overall (based on the best response).

Objective Response Rate Tumor response following the start of Ad-RTS-hIL-12 immunotherapy will be assessed using RECIST v1.1. Overall response at Week 12 is based on the totality of the responses for target and non-target lesions, as shown in the table below:

| Target Lesions | Non-target Lesions | New Lesions | Overall Response |
|-------------------|-----------------------------|-------------|------------------|
| CR | CR | No | CR |
| CR | Non-CR/non-PD | No | PR |
| CR | Not evaluated | No | PR |
| PR | Non-PD or not all evaluated | No | PR |
| SD | Non-PD or not all evaluated | No | SD |
| Not all evaluated | Non-PD | No | NE |
| PD | Any | Yes or No | PD |
| Any | PD | Yes or No | PD |
| Any | Any | Yes | PD |

The ORR is defined as the percentage of subjects who have CR or PR at 12 weeks. The ORR will be summarized by HER2 status group and overall. An exact 2-sided 95% confidence interval will also be presented by HER2 status and overall.

For this calculation, responders are defined as those experiencing a CR or a PR. Non-responders are those either with stable or progressive disease. Those subjects who cannot be assessed will be treated as non-responders for the purposes of deriving the percentage of responders and confidence intervals. In addition, the number of subjects whose baseline tumor status (stable disease or PR) improves to PR or better at 12 weeks following the start of Ad-RTS-hIL-12 immunotherapy with RECIST v1.1 will be listed and summarized by HER2 status and overall.

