8.4 Study Endpoints

8.4.1 Primary Efficacy Endpoint

The primary efficacy endpoint is the 16-week PFS rate, calculated as the number of subjects who had not progressed or died prior to 16 weeks from the date of their first dose, divided by the number of subjects in the study arm. Subjects who neither progressed nor died, but had their last tumor assessment prior to 16 weeks, will not be categorized as progression-free and will not be included in the numerator. Progressive disease (PD) will be determined by mRECIST v1.1 (please refer to [Appendix 4](#)).

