5.1.2. Secondary Endpoints

Secondary endpoints are as follows:

- The proportion failed by 12 weeks is denoted as the progression rate survival and is derived based on the sum of progression events, death events, and subjects who discontinue the trial due to an Adverse event (AE).
- The ORR, defined as the rate of CR plus the rate of PR at 12 weeks following the start of Ad-RTS-hIL-12 immunotherapy
- The DCR, defined as the proportion of subjects who have a CR, PR, or stable disease at 12 weeks following the start of one cycle of Ad-RTS-hIL-12 immunotherapy
- The number of subjects whose baseline tumor status (stable disease or PR) improves to PR or better at 12 weeks following the start of Ad-RTS-hIL-12 immunotherapy
- The radiographic responses by irRC with conventional reporting by RECIST
- Tumor and serum immune biomarkers

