10.2. Disease Control Rate

The DCR is the proportion of subjects who have a CR, PR, or stable disease at 12 weeks following the start of Ad-RTS-hIL-12 immunotherapy using RECIST v1.1.

The DCR will be summarized by HER2 status group and overall. An exact 2-sided 95% confidence interval will also be presented.

For this calculation, responders are defined as those experiencing a CR, PR, or stable disease. Non-responders are defined as those with PD. Those subjects that cannot be assessed will be treated as non-responders for the purposes of deriving the percentage of responders and confidence intervals.

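### The SAP's 12-week progression rate keeps fully dosed subjects lost for non-AE reasons in the denominator without counting them as failed, while ORR and DCR score the same subjects as non-responders

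*SAP*

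**What the plan says.** **Numerator.** SAP 10.1 says the proportion failed by week 12 is "derived based on the sum of progression events, death events, and subjects who discontinue the trial due to an AE". SAP 5.1.2 gives the same three components. Neither section mentions consent withdrawal, loss to follow-up, other non-AE exits or a missing week-12 scan.

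**Denominator.** SAP 10.1: "The progression rate will be summarized by HER2 status group and overall for the evaluable population". SAP 6.2 defines three populations, and only one has evaluable in its name: "The veledimex-evaluable population will comprise subjects who have received the injection of Ad-RTS-hIL-12 and all 7 doses of veledimex". It does not require any scan after baseline.

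**Missing data.** SAP 6.3 states that, unless otherwise specified, "missing responses will be included in both the display and in the calculation of percentages". It also says "No imputations for missing or partial data will be made".

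**Neighbouring rates.** For DCR, SAP 10.2 says "Those subjects that cannot be assessed will be treated as non-responders". The ORR text in SAP 10.1 has an equivalent rule. SAP 10.4, the proportion progression-free at week 12, has no rule for subjects who cannot be assessed. SAP 5.4 says progression-free survival will be analysed by Kaplan-Meier, but section 10 does not specify such an analysis.

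**Protocol, for contrast only.** In section 8.4.1, a subject with neither progression nor death whose last tumour assessment came before week 16 "will not be categorized as progression-free and will not be included in the numerator".

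**The concern.** The list of failure events is closed, and the denominator depends only on dosing. A subject who receives the injection and all seven veledimex doses, then leaves for a non-AE reason with no progression on record, adds one to the denominator and nothing to the numerator. Arithmetically that subject is treated like one shown to be progression-free. The SAP took the opposite line for ORR and DCR in the same part of the document.

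The progression rate is the first secondary objective and endpoint listed, and the precision statement in SAP 5.4 is built on it. The study described in the SAP has one arm, so no comparator carries the same distortion. SAP 5.2 counts early resumption of chemotherapy as failure when progression is unequivocal; departures for other reasons have no corresponding rule. How often they would occur is not stated.

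**Working it through.** **1. The plan's own precision figure.** SAP 5.4 gives a maximum of 40 treated subjects and a maximum exact 95% half-width of 0.16. The exact two-sided (Clopper-Pearson) limits for x events in n are:

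- lower: the 0.025 quantile of Beta(x, n − x + 1)
- upper: the 0.975 quantile of Beta(x + 1, n − x)

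With n = 40 the interval is widest at x = 20: 0.338 to 0.662, half-width 0.162. This rounds to the stated 0.16, so the figure reproduces.

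**2. Three ways of handling losses.** Let N be the evaluable subjects, F the counted failures (progression, death, AE discontinuation), and L the fully dosed subjects lost for other reasons, or without a week-12 scan, and with no documented progression.

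- As written: F / N
- Losses excluded: F / (N − L)
- Losses counted as failed: (F + L) / N

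The true number failed lies between F and F + L, so F / N is the lowest possible value. The gap between the first and third is L / N.

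**3. Numbers.** Assume all 40 treated subjects are evaluable, so N = 40 and each loss is worth 1/40 = 2.5 points. For L = 2, 4, 6, 8 the gap is 5, 10, 15 and 20 points. With an assumed F = 16 and L = 4:

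| Handling of losses | Calculation | Rate | Exact 95% CI |
|---|---|---|---|
| As written | 16/40 | 40.0% | 24.9 to 56.7 |
| Excluded | 16/36 | 44.4% | 27.9 to 61.9 |
| Counted as failed | 20/40 | 50.0% | 33.8 to 66.2 |

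Over F = 12 to 24 and L = 2 to 8, the gap between exclusion and the rule as written runs from 1.6 points (12/38 = 31.6% against 12/40 = 30.0%) to 15.0 points (24/32 = 75.0% against 24/40 = 60.0%). If N is below 40, each loss weighs more than 2.5 points.

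**4. Against DCR.** In the same example, suppose all 16 failures are progression or death and the other 20 subjects have CR, PR or stable disease. If DCR uses the same 40 subjects (SAP 10.2 does not name its population), DCR = 20/40 = 50%, so 1 − DCR = 50%. The progression rate is 40%. The 10-point difference is the four lost subjects: disease not controlled in one rate, not failed in the other.

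**The case against.** Several counter-arguments narrow the point.

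- **Not every early loss is affected.** A reader might infer that anyone lost before week 12 is scored as not failed. A subject who stops before the seventh dose is outside the veledimex-evaluable population and is dropped altogether, as is a subject who stops for an AE during dosing. The point covers losses after dosing is complete.
- **The SAP never says a lost subject is a success.** SAP 10.1 uses the word evaluable without the full population name, and SAP 6.3 would display missing responses. If a week-12 assessment was meant to be required, losses would be excluded. The SAP does not say that, and a displayed missing category does not change F / N.
- **Three rates in conflict is not shown.** SAP 10.4 has no rule for losses, so the week-12 PFS rate is undetermined for them. The demonstrable contrast is with ORR and DCR. Even there, the progression rate and DCR need not sum to 100%: an AE discontinuation is a failure in the first but not, by itself, a non-response in the second.
- **The reference is a convention.** Counting every loss as failed is the worst case, not the truth. Against exclusion, the four-loss example differs by 4.4 points, not 10.
- **Protocol 8.4.1 does not govern this SAP.** It is tempting to read the SAP as breaking the protocol's rule. However, the SAP describes a single-arm, single-center, one-cycle Phase Ib/II study with a 12-week endpoint; the protocol describes a randomized multicenter Phase II study with a 16-week endpoint. The SAP also cites protocol sections absent from the supplied protocol, and its own protocol may say more about losses.
- **No decision hangs on the rate.** It is secondary, with no null threshold. The Kaplan-Meier analysis in SAP 5.4 would censor losses, but it concerns PFS, is not carried into section 10, and leaves the 10.1 rate as it is.

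These limits fix the scope and size of the point. They do not remove the mismatch within the SAP.

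**Conclusion.** The point holds within that scope. Read together, the closed numerator, the dosing-based denominator and the missing-data rules leave a fully dosed subject with a non-AE loss or no week-12 scan, and no documented progression, in the denominator and outside the failures. The SAP's own ORR and DCR rules count that subject against treatment. The progression rate as written is therefore the most favourable figure compatible with the counted events.

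The size depends on the number lost, which the documents do not give: 2.5 points per loss against counting losses as failed if all 40 are evaluable, and less against exclusion. The conclusion also assumes that the evaluable population in SAP 10.1 is the veledimex-evaluable one. The change should be made, but no pass/fail decision in the SAP depends on it.

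**What to change.** 1. In SAP 10.1 and 5.1.2, name the denominator by its full defined title.
2. State that any subject in that population without a documented progression-free assessment at week 12 counts as failed, as ORR and DCR already do for subjects who cannot be assessed. Mark this as an exception to the no-imputation statement in SAP 6.3.
3. Apply the same rule to the week-12 PFS rate in SAP 10.4.
4. Carry the Kaplan-Meier analysis from SAP 5.4 into section 10 as a sensitivity analysis, with losses censored, and report the number lost beside each rate.

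The cost is a few sentences. Reasons for discontinuation are already to be tabulated under SAP 7. The rate may look slightly less favourable, and some subjects who were in fact progression-free when lost will count as failed; the sensitivity analysis shows how far that matters.
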